ADHD findings affect the behavioral, emotional, academic, social and cognitive functions of children, and behavioral outcomes that are not compatible with the age of the children can be observed. These symptoms significantly affect children's activities of daily living, academic skills and social participation. In addition, because it continues throughout life, it negatively affects the quality of life of family members such as parents, siblings, and caregivers (4).

Given the multidimensional nature of ADHD, current research has largely focused on cognitive and behavioral skills related to attention and executive functions, or social behavioral skills such as social participation and impulsivity, but insufficient attention has been paid to sensorimotor skills. However, the literature indicates the presence of sensory integration problems in children with ADHD. Sensory integration is defined as the neurological process in which the person processes the sensory experiences from the body and the external environment in a way that allows the body to be used meaningfully and purposefully (5). This process consists of different steps in which the central nervous system recognizes, organizes, perceives, interprets and responds to sensory information (6). Sensory integration disorder (DDD) is the general descriptive expression used for the processing problem in one or more of these steps. Researchers divide DDD into two basic classes as sensory modulation and sensory perception-based disorders (7).

Sensory modulation disorder has two basic manifestations: above-normal reactivity (defensive and avoidant responses) and below-normal reactivity (poor recording). Difficulties in attention, emotion regulation, and activity, avoidance of sensory experiences, sensory seeking, and poor self-esteem are behavioral traits that can be seen in individuals with sensory modulation difficulties. Sensory perception-based disorders are; poor postural-ocular control, sensory discrimination, body awareness, difficulties with vestibular-based bilateral integration and sequencing, and somatodyspraxia. Behavioral consequences of sensory integration disorders based on sensory perception can be seen as poor self-esteem or self-efficacy, avoidance of motor activities, weak fine and gross motor skills, visual-motor coordination and organizational skills, and sensory seeking (7). Sensory modulation problems are determined by family interviews and caregiver scales (Sensory Profile or Sensory Processing Scale), while sensory perception-based difficulties are determined by standard tests (Sensory Integration and Praxis Test) and in some cases, caregiver scales (8).

In the 1950s, Jean Ayres developed the theory of sensory integration and defined typical sensory development, defined sensory integration disorder in which we defined atypical sensory-behavioral responses, assessment tools and the way of applying Ayres Sensory Integration therapy (5, 9). In studies on Ayres Sensory Integration therapy, it is stated that when the intervention results are examined, improvement is observed in the areas of sensory, motor, cognitive, behavioral, social participation, and operational performance (10).

Many studies conducted with individuals with ADHD report that their ability to perceive and process sensory information is affected (11-14). In addition, it has been shown that children with ADHD have difficulties in producing appropriate sensory responses at school, at home and in social environments in relation to their sensory processing difficulties (11), and these difficulties cause problems in daily living activities and performance in children (15, 16).

In studies conducted with children with ADHD, the presence of problems related to sensory processing was determined by both behavioral and neurophysiological measurements. Electroderm In a study conducted with skin responses, it was found that children with ADHD had more sensory reactivity responses than the control group (12). Another study conducted with EEG showed that children with ADHD with tactile sensitivity and children with ADHD without ADHD differ in the processing of somatosensory brain areas (13). Studies evaluating behaviors have revealed results that support these neurophysiological findings. Dunn and Benett's study using the Sensory Profile (DP) family scale revealed that individuals with ADHD differ in all 14 subtest sections of the DP family scale, including hearing, touch, multi-sensory processing, emotional/social responses, and behavioral outcomes (11). In another study conducted with the same scale, individuals with ADHD showed higher sensory reactivity responses than their controls, supporting previous findings (14). Although there are many studies using family scales such as DP, which measures sensory modulation skills in individuals with ADHD, there are limited studies evaluating sensory perception and sensory perception-based problems. In another study, individuals with ADHD had lower scores in the somatosensory perception tests of the DBPT when compared to the healthy group, and it was revealed that these individuals had a weak tactile and proprioceptive perception (13).

Although there are studies in the literature showing the presence of DDD in children with ADHD, most researchers have studied a similar profile, such as sensory modulation disorder, and few have investigated all components of sensory integration (such as sensory perception, praxis) (17). More research is needed to confirm the effects of Ayres Sensory Integration therapy in children with ADHD and the possible relationship between DDD-based difficulties in activities of daily living and ADHD symptoms. In our study, it was aimed to investigate the effect of Ayres Sensory Integration therapy on sensory, motor, cognitive, behavioral and social participation in children with ADHD in the light of extensive literature and recommendations.

3. Benefits and Risks Expected from Study

The evaluations to be made within the scope of the study do not involve any risk. At every moment of Ayres Sensory Integration Therapy applications, there will be at least one researcher, including our volunteer child and their parents. Considering all this information, participation in our study does not pose a risk. Difficulty with sensory and motor skills is a common problem for children with attention deficit hyperactivity disorder. With a structured sensory integration therapy application, it is aimed to reduce the sensory, motor and cognitive difficulties of children in their daily lives.

4. Materials and Methods

4.1. Study Place:

In this research, PhD student [name], [name] [name], [name]. [name] and [name]. [name] will take part in the evaluation, data analysis and writing stages. The research will take place in the pediatric rehabilitation unit of Hacettepe University, Department of Occupational Therapy.

4.2. Time to Study:

The study is planned to be completed between February 2023 and April 2024, starting immediately after the approval of the ethics committee.

4.3. Study Population, Sample, Research Group:

Study group and control group will be compared in the research. The change between the last evaluation and the first evaluation will be calculated and a comparison of this change between the two groups will be made. T-test will be used in independent groups for this comparison. The effect size was predicted to be 0.8. With 5% margin of error and 80% power, the sample size was calculated as (45 + 45) 90 for the groups. Participants will be divided into two groups as training group and control group. All volunteering children will be included in the study, taking into account the inclusion and exclusion criteria.

Inclusion criteria:

- a. To be in the age range of 6-8,
- b. Being diagnosed with Attention Deficit Hyperactivity Disorder according to the DSM-V criteria,
- c. Continuing school education,
- d. Having agreed to participate in the study after being informed about the research.

Exclusion criteria:

Children with additional physical and neurological problems will be excluded from the study.

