intervention. It provides the child's continuous interest in the set goals and offers a person-centered approach (39). The determined goals should be specific, measurable, achievable, relevant and well-timed (40). While applying GAS, goals are set for the child and possible outcomes are defined for each goal. After a certain intervention, the functional status of the child is determined again. GAS consists of 5 points as -2, -1, 0, +1 and +2. A score of -2 indicates the child's pre-intervention baseline level, a score of -1 indicates a development below the expected attainment level, a score of 0 indicates an expected attainment level, a score of +1 indicates a better-than-expected achievement, and a score of +2 indicates that the child performs much better than expected (39, 40).

4.7. Collection of Data:

The data will be collected by the occupational therapist from the volunteer participants by face-to-face interview method, and consent and evaluation forms will be collected.

4.8. Intervention Program:

Individuals will be interviewed for the Informed Consent Form. Consent will be obtained from each individual who volunteers to participate in the study. Consent forms will be given in writing and will be requested back once signed.

Participants signing the Informed Consent Form will form the working group, taking into account the inclusion and exclusion criteria. This study group will be divided into two as training and control groups by simple randomization method. After the training and control groups are determined as a result of randomization, an initial evaluation will be made for all participants separately. Ayres Sensory Integration Therapy will be applied to the training group for 10 weeks, 3 days a week (30 sessions), 60 minutes per session. Final assessments will be made at week 11 of therapy. In the control group; An appointment will be made 10 weeks after the initial assessment. After 10 weeks, final evaluations will be made for control. After the final evaluation, 30 sessions of Ayres Sensory Integration Therapy will be applied for 10 weeks, 3 days a week, similar to the control group. In the Ayres Sensory Integration Therapy application, the therapist will provide interviews with the child and their parents in structured environments, and the parents will be asked to repeat the session by explaining the goals in an explanatory way after the session.

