[figure not shown]
As descriptive statistics in the study; Frequency (n) and percentage (%) values will be used in the evaluation of categorical variables. Shapiro-Wilk and Kolmogorov-Smirnov normality tests will be used for the conformity of numerical variables to the normal distribution, and as descriptive statistics; Mean±standard deviation values will be given for the variables suitable for normal distribution, and median (minimum-maximum) values will be given for those that do not comply with the normal distribution. The appropriate hypothesis testing method planned to be used in the study was determined as "Two-Way Analysis of Variance with Repetitions on a Single Factor" when parametric test assumptions were met. If the parametric test assumptions for the relevant test are not met, whether there is a difference between the groups in terms of quantitative variables, with the "Student t test" when the parametric test assumptions are met, and with the "Mann-Whitney test" if they are not; In examining whether quantitative variables change according to three separate evaluation times, "Repeated measures variance analysis" will be used when the test assumptions are met, and "Friedman test" if it is not provided. Type I error probability will be taken as $\alpha=0.05$ in all hypothesis tests and SPSS v25.0 package program will be used for statistical evaluations. While calculating the sample size required to test the research hypothesis, the effect widths defined by Cohen* were used and the calculations were made with the G*Power 3.1.9 program.

The minimum sample size required for the study is 90 people in total, approximately equally distributed in the groups that will provide 90% test power at 95% confidence level, with the effect width $f=0.30^*$ for "Two-Way Analysis of Variance in Repeated Measurements with Repetitions on a Single Factor".

F tests - ANOVA: Repeated measures, between factors

Analysis: A priori: Compute required sample size

Input:	Effect size f	=	0,3
	α err prob	=	0,05
	Power ($1-\beta$ err prob)	=	0,9
	Number of groups	=	2
	Number of measurements	=	2
	Corr among rep measures	=	0,5
Output:	Noncentrality parameter λ	=	10,8000000
	Critical F	=	3,9493210
	Numerator df	=	1,0000000
	Denominator df	=	88,0000000
	Total sample size	=	90
	Actual power	=	0,9015268

6. Bibliography

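### The planned treatment comparison is valid but ignores the initial score as a covariate; adjusting for it would cut the variance by about a quarter at the plan's input correlation of 0.5

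*Combined protocol and SAP*

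**What the plan says.** Section 4.3 builds the comparison on differences within each child: "The change between the last evaluation and the first evaluation will be calculated". The two arms are then set against each other on that difference, and the method is specified: "T-test will be used in independent groups for this comparison". That section assumes an effect of 0.8, with 45 children per group.

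Section 5 names a different procedure, "Two-Way Analysis of Variance with Repetitions on a Single Factor", for use when parametric assumptions are met. Student t or Mann-Whitney serve as between-group fallbacks. It does not say which term of the ANOVA carries the treatment comparison. Its sample-size output uses two groups, two measurements, f = 0.30 and a value of 0.5 for "Corr among rep measures".

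Section 4.8 supplies the baseline data: after randomisation, "an initial evaluation will be made for all participants separately". Section 4.6 describes the Goal Attainment Scale (GAS) so that -2 is each child's pre-intervention level. No section mentions a baseline covariate or ANCOVA.

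**The concern.** A change score fixes the slope of final on initial score at 1. When SDs are equal before and after, the efficient slope equals the correlation, which the plan itself sets at 0.5. Subtracting the whole initial score then adds noise to the comparison. It also over-corrects when the arms differ by chance at baseline. None of this depends on dropout; it remains if all 90 children are evaluated twice.

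Precision is at stake, not validity. In a randomised comparison with a clean baseline, both analyses target the same group difference, and the adjusted one has the smaller standard error. Each child completes a long assessment battery, and each treated child attends 30 sessions before the final evaluation. An analysis that makes full use of those data costs nothing extra.

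**Working it through.** **Inputs from the documents.** N = 90 (45 + 45), effect 0.8 (section 4.3); alpha 0.05, f = 0.30, two measurements, rho = 0.5 (section 5).

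**Assumptions.** Two-sided tests, equal SDs at both evaluations, complete data. The effect d is the final-evaluation difference in SD units. At rho = 0.5 the SD of change equals the raw SD, because 2(1 - 0.5) = 1, so it makes no difference at that correlation which SD standardises the 0.8.

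**1. The plan's own output.** For the between-factors effect, lambda = f² x N x m / (1 + (m - 1) x rho) = 0.09 x 90 x 2 / 1.5 = 10.8. The critical F(1, 88) is 3.949 and power is 0.9015. This reproduces exactly.

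**2. Equivalence of the two planned analyses.** With two groups and two evaluations, the group x time F equals the square of the change-score t. This holds only for that term and only with two evaluations.

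**3. Variance ratio.**
- Change score: variance proportional to 2(1 - rho).
- ANCOVA: variance proportional to 1 - rho².
- Ratio: (1 - rho²) / (2(1 - rho)) = (1 + rho)/2.

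| rho | ANCOVA / change-score variance |
|---|---|
| 0.3 | 0.65 |
| 0.5 | 0.75 |
| 0.7 | 0.85 |
| 0.8 | 0.90 |

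Estimating the slope with 90 children raises 0.75 to about 0.76; a 40,000-run simulation gave 0.757. At rho = 0.5, 90 children analysed by change score carry the information of about 90 x 0.75 = 67.5 analysed by ANCOVA.

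**4. Power with 45 per arm at rho = 0.5.** Change score: lambda = d² x (90/4) / (2(1 - rho)) = 22.5d², on 1 and 88 df. ANCOVA: lambda = d² x 22.5 / (1 - rho²) = 30d², on 1 and 87 df.

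| d | Source | lambda, change | Power, change | lambda, ANCOVA | Power, ANCOVA |
|---|---|---|---|---|---|
| 0.8 | section 4.3 | 14.4 | 96.4% | 19.2 | 99.1% |
| 0.6 | assumption | 8.1 | 80.4% | 10.8 | 90.1% |
| 0.5 | assumption | 5.625 | 65.0% | 7.5 | 77.3% |

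The simulation at d = 0.6 gave 80.2% and 89.8%; it includes the small cost of estimating the slope.

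**5. Chance imbalance.** With 45 per arm, the SE of the baseline difference is sqrt(2/45) = 0.211 SD. A gap of at least 0.3 SD in either direction has probability 2(1 - Phi(0.3/0.211)) = 15.5% for each outcome. At rho = 0.5, a 0.3 SD gap moves the expected change-score difference by 0.3 x (1 - 0.5) = 0.15 SD. ANCOVA removes this shift in expectation.

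**The case against.** **The gain is small at the stated effect.** This stands. At 0.8, power is already 96.4% and rises by less than 3 points. The change-score test is also valid and unbiased over randomisation. The case rests on precision, on chance imbalance, and on the possibility that the true effect is smaller.

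**Tempting reading: the plan's own inputs give 80% versus 90% power.** A reader might convert f = 0.30 to d = 0.6 and conclude this. The documents do not support it. The f was entered for a between-factors main effect, where 2f = 0.6 is the group difference averaged over both evaluations. With equal baselines, that implies 2 x 0.6 = 1.2 SD at the final evaluation, where change-score power at rho 0.5 exceeds 99.9%. The 0.6 SD row is therefore only an assumption.

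**Tempting reading: the shared noncentrality of 10.8 means ANCOVA delivers the stated 90%.** The match is a coincidence of rho = 0.5. The plan's formula gives 0.09 x 90 x 2/(1 + rho); ANCOVA with d = 2f gives 0.09 x 90/(1 - rho²). At rho = 0.3 these are 12.5 and 8.9; at 0.7 they are 9.5 and 15.9. The software was run for a different test.

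**The correlation of 0.5 is a software input, not evidence about these scales.** This stands. No outcome-specific correlation is given, and at rho = 0.8 the variance reduction is only 10%.

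**The ANOVA may not be the group x time test.** This also stands. Section 5 names no term, powers the main effect, and elsewhere mentions three evaluation times. The main-effect reading would not help the plan, however. It averages baseline with follow-up, so it sees half the final difference: at d = 0.6 and rho = 0.5, lambda = 0.3² x 22.5/0.75 = 2.7 and power is about 37%. The group x time reading is the favourable one.

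**The baseline follows randomisation, and several scales are parent-reported.** If knowledge of allocation shifts the initial ratings, both methods are affected and they no longer estimate the same quantity. This is a condition on the fix, not an argument for change scores.

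**Conclusion.** The point holds as one of efficiency. The planned comparison makes no baseline adjustment although the initial scores are collected. With equal SDs before and after, ANCOVA has 0.75 of the change-score variance at rho 0.5, and 0.65 to 0.90 across rho from 0.3 to 0.8. The power gain is 96.4% to 99.1% at the section 4.3 effect. It reaches 10 to 12 points only if the true final difference is 0.5 to 0.6 SD, which the documents do not state. GAS is outside the point, because its initial score does not vary. The planned test is not invalid, and the documents do not show that the stated power fails because of this choice. The change is worth making because it costs nothing, but it does not decide whether the trial is sound.

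**What to change.** In sections 4.3 and 5, use one treatment comparison for each outcome except GAS: a linear model of final score on group with the initial score as covariate, reporting the adjusted group difference with its 95% CI. In addition:

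- Where normality fails, keep the baseline-adjusted model with robust or bootstrap standard errors, or use a rank-based ANCOVA, in place of the unadjusted Mann-Whitney test.
- Compare GAS between groups without a baseline covariate.
- Keep the change-score t-test as a sensitivity analysis.
- Add no further covariate, such as age, unless it is fixed in advance.
- State that the adjustment assumes initial ratings are unaffected by knowledge of allocation, because the initial evaluation follows randomisation.

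The cost is protocol and SAP wording and one degree of freedom per model. The linear model runs in the SPSS v25.0 package already named. No extra children, visits or instruments are needed.

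### Section 4.3's sample-size statement does not follow from its own inputs: an effect of 0.8 at 5% error and 80% power needs 26 children per group (52), not 45 + 45 = 90

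*Combined protocol and SAP*

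**What the plan says.** Section 4.3 (Study Population, Sample, Research Group) defines the comparison as the change from first to last evaluation, compared between the two groups. It names the test ("T-test will be used in independent groups for this comparison") and the effect ("The effect size was predicted to be 0.8"), and then gives the result: "With 5% margin of error and 80% power, the sample size was calculated as (45 + 45) 90 for the groups". It does not state the metric of the 0.8, the sidedness or any allowance for loss.

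Section 5 (Statistical Analysis of Data) gives a second justification for the same total: "The minimum sample size required for the study is 90 people in total", in groups "that will provide 90% test power at 95% confidence level", with f = 0.30. The G*Power output printed there is headed "F tests - ANOVA: Repeated measures, between factors" and uses two groups, two measurements and a correlation of 0.5. Section 5 also says: "Type I error probability will be taken as $\alpha=0.05$ in all hypothesis tests".

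**The concern.** An effect of 0.8 is large for a two-group t-test, and 45 per group is far more than it needs at 80% power. The effect size, the power and the N in section 4.3 therefore do not fit together on the ordinary reading.

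This matters because 4.3 is the only place that sizes the comparison of change. As it stands, a reader cannot tell what difference the trial was planned to detect, and so cannot judge a null result or the justification for enrolling 90 children. The matching total in section 5 makes this harder to see. The two sections seem to confirm each other, yet they differ in effect size, power and test.

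**Working it through.** **Inputs.** From 4.3: independent-groups t-test on change, effect 0.8, error 5%, power 80%, stated result 45 + 45. From 4.4: equal allocation. From section 5: alpha 0.05 for all tests; f = 0.30, power 0.90, two measurements, correlation 0.5. Assumptions: 0.8 is Cohen's d (difference in mean change divided by the SD of change), and the test is two-sided. One-sided is also shown.

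**Formula.** For n per group, the power is that of a noncentral t with 2n − 2 degrees of freedom and noncentrality d·√(n/2).

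**Trying to reproduce 4.3.**

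| Effect d | Sides | n per group | Power |
|---|---|---|---|
| 0.8 | 2 | 25 | 0.791 |
| 0.8 | 2 | **26** | 0.807 |
| 0.8 | 1 | 20 | 0.799 |
| 0.8 | 1 | **21** | 0.817 |
| 0.8 | 2 | 45 (as stated) | **0.964** |

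The requirement is 2 × 26 = 52 two-sided, or 2 × 21 = 42 one-sided. The stated 90 is not reproduced.

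**What would be needed to reach 45 per group with d = 0.8?**
- Higher power: 90% needs 34 per group and 95% needs 42.
- Dropout: 1 − 26/45 = 42%. None is stated.
- Multiplicity: alpha would have to be about 0.004. Section 5 sets 0.05 throughout.
- Mann-Whitney instead of the t-test: 28 to 31 per group at 80% power, using efficiencies of 3/π and 0.864.

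**Which effect does fit 45 per group at 80% power?** With d = 0.6, n = 44 gives 0.795 and n = 45 gives 0.804. Only effects from 0.597 to 0.604 make 45 the minimum. For two equal groups f = d/2, so section 5's f = 0.30 corresponds to d = 0.6 per measurement. This is a clue to the origin of the figure, not proof.

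**Reproducing section 5.** The noncentrality is λ = N·f²·m/(1 + (m − 1)ρ) = 90 × 0.09 × 2/1.5 = 10.8. The critical F(1, 88) is 3.9493 and the power is 0.9015, as printed; N = 88 gives 0.895. The calculation is right for what it is labelled: the between-groups main effect averaged over the two measurements. That is a different effect from the difference in change. The same test at 80% power needs N = 68. With 0.8 entered as f = 0.40 it needs N = 40 (80%) or 52 (90%), so that route does not link 0.8 to 90 either.

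**What 45 per group does support** (two-sided 5% t-test on change): a detectable effect of 0.597 SD of change at 80% power and 0.691 SD at 90%.

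**The case against.** The strongest reply is that 4.3 never names the metric of its 0.8. If it is in SDs of the raw score, the effect on change is 0.8/√(2(1 − ρ)), where ρ is the correlation between first and last evaluation. That gives 51 per group at ρ = 0, 46 at 0.10, 45 at about 0.105 to 0.12, 44 at 0.13, and 26 at 0.5. So there is a reading under which effect, power and N agree. It needs a narrow range of correlation that appears nowhere in the documents, and the only correlation they state, 0.5, leads back to 26. What stands is that the inconsistency is established for the standard reading, and the authors should be asked for the metric.

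Two further points are fair. The 0.6 explanation is a reconstruction, because the documents never give 0.6 as a planned effect; it can only be a candidate. And although section 5's output is not a valid basis for the comparison of change, that does not show where the authors took 90 from; it may have been carried over from there.

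It can also be said that the consequences are small, since the trial is larger than 4.3's inputs require. That limits the remedy to wording. It does not make the stated calculation correct.

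**Conclusion.** The concern holds. On 4.3's stated inputs, with 0.8 read as Cohen's d on change and a two-sided test, the requirement is 52 children rather than 90, and power at 90 is about 96% rather than 80%. A one-sided test widens the gap (42). No allowance in the documents closes it. Which input is at fault cannot be settled from the documents: it may be the 0.8, its metric, or the stated power. Section 5's 90% power does not settle it, because it belongs to another effect. The arithmetic is certain under the assumptions named; the explanation for the discrepancy is not. This should be fixed as an error in a stated figure. It is not a case for changing N.

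**What to change.** Keep N = 90.

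1. In 4.3, replace the sample-size sentence with: *With 45 children per group analysed and a two-sided 5% independent-groups t-test on change, the detectable effect is 0.60 SD of change at 80% power and 0.69 SD at 90% power.* As a statement of what 45 analysed per group can detect, this is true whichever input was wrong. It refers to children analysed, so any expected loss must be stated separately.
2. If the authors confirm that 0.8 is the predicted difference in mean change divided by the SD of change, add: *Power for the predicted 0.8 is about 96%.* Otherwise they should correct the 0.8, or state its metric, the sidedness and the correlation used.
3. In section 5, add: *The f = 0.30, the 90% power and the minimum of 90 apply to the between-group main effect averaged over the two measurements; they are not the power or sample size for the comparison of change in section 4.3.*

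The cost is one sentence replaced, one conditional sentence, one sentence added, and a check by the authors of which effect size they entered. Section 5's output, the design and the conduct of the trial do not change.
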